## 4 Study population

Screening procedures must have been performed within 14 days before the first dose of study drug.

### 4.1 Inclusion criteria

#### **Inclusion criteria for both escalation and expansion phase:**

- Ability to understand and the willingness to sign a written informed consent. A signed informed consent must be obtained before screening.
- AML according to WHO-2016 criteria, excluding acute promyelocytic leukemia
- Relapsed from first or second CR after 1-2 cycles of standard induction chemotherapy (which must have included cytarabine with an anthracycline or anthracenedione), including relapse after allogeneic stem cell transplantation (dose escalation and expansion part)
- Age 18-75 years
- Fit for intensive chemotherapy, defined by
  - ECOG 0-2, life expectancy > 3months
  - Adequate hepatic function: ALAT/ASAT/Bilirubin  $\leq 2.5 \times \text{ULN}^*$ 
    - \* unless considered due to leukemic organ involvement

Note: Subjects with Gilbert's Syndrome may have a bilirubin > 2.5  $\times$  ULN per discussion between the investigator and Coordinating investigator.

- Adequate renal function assessed by serum creatinine  $\leq 1.5 \times \text{ULN}$  OR creatinine clearance (by Cockcroft Gault formula)  $\geq 50 \text{ mL/min}$

- Patient is afebrile and hemodynamically stable for at least 72 hours at the time of study medication initiation.
- Male subjects must agree to refrain from unprotected sex and sperm donation from time point of signing the informed consent until 30 days after the last dose of study drug.
- Women must fulfill at least one of the following criteria in order to be eligible for trial inclusion:
  - Post-menopausal (12 months of natural amenorrhea or 6 months of amenorrhea with Serum FSH > 40 U/ml)
  - Postoperative (i.e. 6 weeks) after bilateral ovariectomy with or without hysterectomy
  - Women of childbearing potential must have a negative serum pregnancy test performed within 7 days before the first dose of study drug.
  - Continuous and correct application of a contraception method with a Pearl Index of <1% (e.g. implants, depots, oral contraceptives, intrauterine device – IUD) from time point of signing the informed consent until 30 days after the last dose of study drug.

Note: At present, it is not known whether the effectiveness of hormonal contraceptives is reduced by venetoclax. For this reason, women should use a barrier method in addition to hormonal contraceptive methods.
  - Sexual abstinence
  - Vasectomy of the sexual partner

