	
 
• Rapid recruitment due to commitment of one of the two largest cooperative AML study groups in Germany (for expansion phase) and due to the chemotherapy combination being one of the most commonly used regimens in Germany (and similar to MEC in the US)
 

Endpoints of the Trial	
Primary endpoint phase I
 
Maximum tolerated dose of cytarabine in combination with venetoclax plus mitoxantrone in the framework of a 3+3 design
 
Primary endpoint phase II
 
CR/CRi rate
 
Secondary Endpoints
 
 
• Duration of remission
 
• Cumulative incidence of relapse
 
• Depth of remission (MRD)
 
• Relapse-free survival
 
• Overall survival
 
• Early mortality (within 14 and 30 days)
 
• Proportion of allogeneic stem cell transplantation following response
 
• Tolerability (incidence and grade of adverse events)
 
 
Exploratory endpoints
 
 
• Identification of biological factors predicting CR/CRi achievement
 
• Changes in clonal architecture of hematopoiesis during therapy
 

Main Inclusion Criteria	
Inclusion criteria for both escalation and expansion phase:
 
 
• Signed Informed consent
 
• AML according to WHO-2016 criteria, excluding APL
 
• Hematologically relapsed after first or second CR, including relapse after allogeneic stem cell transplantation
 
• Age 18-75 years
 
• Fit for intensive chemotherapy, defined by 
 
○ ECOG 0-2, life expectancy > 3 months
 
○ Adequate hepatic and renal function (ALAT/ASAT/Bilirubin <math>\leq 2.5 \times</math> ULN;
 
○ Creatinine < 1.5 x ULN OR creatinine clearance by Cockcroft Gault formula <math>\geq 50</math> mL/min)
 
 
 

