In order to avoid undertreatment of patients in the low cytarabine dose levels in the dose escalation part of the trial, only patients relapsing >90 days after previous cytarabine chemotherapy will be allowed into this part of the trial. This is because >90 days after last cytarabine dose, the disease is again considered sensitive to cytarabine, justifying the treatment of patients even with lower cytarabine doses. Patients refractory to standard-dose cytarabine may not be responsive to lower cytarabine doses as given in the first dose levels of this trial and are therefore excluded from enrolment in the escalation part, but not in the expansion part where higher cytarabine doses will be administered.

The benefit for participating patients will be the higher probability to achieve a remission as suggested by 70% remission rates in frail patients with primary AML (Wei et al, 2016). The addition of fixed-dose mitoxantrone ensures a response to treatment even in the initial dose levels. The main risks result from unknown toxicities arising from the combination. However, the known toxicities of venetoclax are hematological in nature. Given that the primary aim of any salvage regimen is to induce a significant blast reduction or morphologic leukemia free state as a prerequisite for the success of further consolidation treatments aiming at inducing a long-term CR, treatment related cytopenias seem to be less important in the setting of relapsed/refractory AML than in primary AML treatment and are intended in AML relapse treatment in order to eradicate the relapsing and supposedly resistant leukemic AML clone. As a result of these considerations, possible benefits of study treatment will outweigh potential risks. Additionally, risks will be minimized by toxicity monitoring and pharmacovigilance measures.

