**Inclusion criteria applying for expansion phase (Phase II) only:**

- Primary refractory after 1-2 cycles of standard induction chemotherapy (100 to 200 mg/m^2 cytarabine over 7-10 days plus anthracycline or mitoxantrone over 3 days) or relapsed from first or second CR after 1-2 cycles of standard induction chemotherapy (which must have included cytarabine with an anthracycline or anthracenedione), including relapse after allogeneic stem cell transplantation

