**4.2 Exclusion criteria**

- Acute promyelocytic leukemia (AML M3)
- CNS involvement or subjects with extramedullary disease only
- Known hypersensitivity to excipients of the preparation or any agent given in association with this study including cytarabine or mitoxantrone
- Intended hematopoietic stem cell transplantation planned as early conditioning from aplasia without previous blood count recovery

- Cumulative previous exposure to anthracyclines of >410 mg/m^2 doxorubicin equivalents
- Acute GVHD ≥ grade 2, extensive chronic GVHD or requiring systemic immunosuppressive therapy within 2 weeks prior to start of study treatment
- HIV infection (due to potential drug-drug interactions between antiretroviral medications and venetoclax, as well as anticipated venetoclax mechanism-based lymphopenia that may potentially increase the risk of opportunistic infections).
- Inability to swallow oral medications
- Any malabsorption condition
- Treatment with strong and moderate CYP3A inhibitors (see [Appendix 1](#)) during screening
- Cardiovascular disability status of New York Heart Association (NYHA) Class ≥ 2.  
Class 2 is defined as cardiac disease in which patients are comfortable at rest but ordinary physical activity results in fatigue, palpitations, dyspnea, or anginal pain.
- Chronic respiratory disease that requires continuous oxygen use.
- White blood cell count > 25 × 10^9/L. Note: Hydroxyurea is permitted to meet this criterion.
- AML relapse treatment with any investigational or commercial drug within 14 days before enrolment. Hydroxyurea is allowed until enrolment to control peripheral WBC counts. Toxic effects of previous investigational drug treatment have to recover to Grade <2.
- Substance abuse, medical, psychological, or social conditions that may interfere with the subject's cooperation with the requirements of the trial or evaluation of the study results
- Pregnant or breastfeeding women.  
Breastfeeding has to be discontinued before onset of and during treatment and should be discontinued for at least 3 months after end of treatment.
- History of active or chronic infectious hepatitis unless serology demonstrates clearance of infection  

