## 6.6 Subject identification and registration

Each subject who signs a consent form for the study and starts any screening procedure will be assigned a unique 6-digit number during the screening period. The first 3 digits are site specific; the remaining 3 digits are subject specific and allocated in a sequential order of subjects starting

the screening period. This screening number will be entered into the eCRF regardless of whether the subject is actually treated with study drug.

On day 1, after completion of screening procedures and prior to first dose of venetoclax, the inclusion and exclusion criteria must be checked. If eligibility is confirmed, the patient will be enrolled in the trial and treatment can be started.

If eligibility cannot be confirmed, the respective patient will be defined as screening failure.

The full patient ID number for trial is composed like this:

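### The more-than-90-days-after-cytarabine limit that section 1.4 sets for the escalation part is missing from the eligibility criteria, so earlier relapses could be enrolled in phase I

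*Protocol*

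**What the plan says.** Section 1.4 (risk-benefit assessment) states the purpose of a restriction, "In order to avoid undertreatment of patients in the low cytarabine dose levels in the dose escalation part of the trial", and then the rule: "only patients relapsing >90 days after previous cytarabine chemotherapy will be allowed into this part of the trial". The reason given is that beyond this interval "the disease is again considered sensitive to cytarabine, justifying the treatment of patients even with lower cytarabine doses". The same paragraph also keeps patients refractory to standard-dose cytarabine out of the escalation part, but not out of the expansion part.

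Section 4.1, under the criteria common to both phases, requires "Relapsed from first or second CR after 1-2 cycles of standard induction chemotherapy", includes relapse after allogeneic transplantation, and adds in brackets that this holds for dose escalation and expansion. The expansion-only list adds "Primary refractory after 1-2 cycles of standard induction chemotherapy". Section 4.2 has one time limit on earlier anti-leukemia treatment: "AML relapse treatment with any investigational or commercial drug within 14 days before enrolment". The synopsis has, for both phases, "Hematologically relapsed after first or second CR, including relapse after allogeneic stem cell transplantation".

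Under section 6.6, on day 1 before the first venetoclax dose, "the inclusion and exclusion criteria must be checked". A patient whose eligibility is confirmed is enrolled and can start treatment.

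**The concern.** Section 1.4 words the 90-day interval as an admission rule, and the ethical argument for the lowest dose levels depends on it. Table 1 gives cytarabine 100 mg/m² at level -1 and 200 mg/m² at level 1, over days 4-10, which is seven days. That lies inside the 100 to 200 mg/m² over 7-10 days that section 4.1 describes as standard induction. The protocol itself regards patients whose disease returned soon after cytarabine as at risk of undertreatment at such levels.

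If the rule is absent from the lists that sites apply, two things are at stake. First, the safeguard in the risk-benefit argument does not operate at the point of enrolment. Second, conduct may differ between sites. One site may apply section 1.4 and another only sections 4.1 and 4.2, and it is unclear whether enrolling an early relapse counts as a protocol deviation.

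**Working it through.** No formula applies and the plan gives no figure to reproduce. The check is a comparison of every place that defines who may enter the escalation part.

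| Place | Relapsed patients: minimum interval since cytarabine | Primary refractory patients in escalation |
|---|---|---|
| Section 1.4 | more than 90 days | not admitted |
| Section 4.1, both phases | none | not listed |
| Section 4.1, expansion only | none | admitted to expansion only |
| Section 4.2 | none (14 days, AML relapse treatment only) | no statement |
| Synopsis, main criteria | none | expansion only |
| Section 3.1 | none | described as part of the phase I population |
| Section 6.6 | refers to the inclusion and exclusion criteria | same |

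1. **Is the limit stated under another name?** The nearest candidate is the 14-day limit in section 4.2. It covers treatment given for the relapse. It says nothing about how long before the relapse the patient last had induction or consolidation cytarabine, so it cannot stand in for the 90-day rule. The sections on design, MTD determination and DLT evaluability (3.1 to 3.2.1) contain no such interval either.

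2. **Was section 1.4 carried into the criteria at all?** In part. It makes two restrictions for the escalation part. The one on refractory disease is carried over, because primary refractory disease appears only in the expansion list. The one on time since cytarabine is not, and the relapse criterion is explicitly marked as common to both parts. This pattern suggests an omission, but it does not prove one.

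3. **Test case.** Take a patient in first relapse 60 days after the last cytarabine dose, with no relapse treatment yet and all other criteria met. Section 4.1: the relapse criterion is fulfilled. Section 4.2: no exclusion on timing since cytarabine applies. Section 6.6: eligibility is confirmed and the patient is enrolled. Section 1.4: 60 is not more than 90, so the patient is not allowed into the escalation part. The two results contradict each other.

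4. **Size.** The synopsis and section 3.1 cap phase I at 18 patients, which corresponds to three levels of six (3 × 6 = 18). The protocol does not say what share of relapses occurs within 90 days of cytarabine. The number affected therefore lies between 0 and 18, and the documents do not allow it to be narrowed.

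5. **Reference date.** Section 1.4 counts the interval once from the previous course of cytarabine chemotherapy and once from the last dose of cytarabine. These can be different dates, so the rule could not be copied into section 4.1 without choosing one.

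**The case against.** The strongest reply is that section 1.4 is itself protocol text in mandatory wording, and section 11.1 demands strict adherence to everything the protocol specifies. Enrolling an early relapse in phase I would then breach the protocol. This stands as far as it goes: a reader might infer that such patients would be enrolled, and the documents support only that they could be. It does not remove the contradiction, because section 6.6 ties enrolment to the criteria lists and those lists would not catch the case.

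Section 1.4 also says that fixed-dose mitoxantrone secures a response even at the initial levels. That tempers the undertreatment worry but does not withdraw the restriction, which stands in the preceding paragraph.

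The synopsis gap adds little by itself. Its list covers main criteria only and refers to section 4.1 for the exact list. The gap that counts is in sections 4.1 and 4.2.

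Two stronger readings are tempting and fail. A reader might infer that every group section 1.4 keeps out of escalation falls through. In fact the eligibility lists do keep primary refractory patients out. A reader might also infer that the primary efficacy analysis is distorted, since the full analysis set takes in phase I patients treated at the MTD (section 8.2.2.1). Section 1.4 limits the escalation part only. The expansion criteria admit relapses at any interval and primary refractory patients as well, so early relapses are not foreign to the full analysis set. The reason given also concerns the low cytarabine levels, not whichever level becomes the MTD.

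**Conclusion.** The protocol contradicts itself on an operative eligibility rule. Section 1.4 admits to escalation only relapses more than 90 days after cytarabine; sections 4.1 and 4.2, which decide enrolment, set no interval. Patients relapsing within 90 days could be enrolled in phase I although the risk-benefit assessment bars them. The number is unknown and at most the 18 phase I patients, a ceiling and not an estimate.

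The conclusion rests on one assumption, which section 6.6 supports: sites decide eligibility from the criteria lists and not from the rationale chapter. The consequence is a patient-protection safeguard that is not enforced and a deviation that is not clearly defined. The sponsor should correct it. No effect on the sample size, the primary test or the case mix of the full analysis set is claimed.

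**What to change.** Reconcile section 1.4 with sections 4.1 and 4.2 and the synopsis. There are two ways, and the documents do not settle which is right:

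- Enter the restriction of section 1.4 in section 4.1 and the synopsis under a heading for the escalation phase only, with a single defined reference date for the start of the interval.
- Remove the restriction and its justification from section 1.4, and revise the risk-benefit argument for the low cytarabine levels so that it no longer relies on it.

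In either case, align the description of the phase I population in section 3.1, which currently includes refractory patients. The cost is one criterion or one paragraph in the next amendment. If the restriction is kept, phase I accrual may be slightly slower.

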## 3 Study design

### 3.1 Design overview

This is an open-label Phase I dose-escalation study of oral venetoclax in combination with increasing cytarabine doses plus mitoxantrone to define the safety profile and MTD of cytarabine in subjects with a histologically or cytologically confirmed acute myeloid leukemia who are refractory or suffered a relapse. This study will be conducted at multiple centers in Germany.

This study will investigate the combination of a fixed maximum venetoclax dose with increasing cytarabine doses plus mitoxantrone in a fixed dose. The venetoclax dose of 400 mg will be reached by a ramp up over 4 days (see Table 2). Parallel chemotherapy with cytarabine will start on day 4. This dose escalation part will enroll a maximum number of 18 patients.

The decision to escalate to the next dose level will be taken by telephone conferences (safety calls) with participation of the investigators, pharmacovigilance and the sponsor (steering committee) on a regular basis.

AbbVie as the manufacturer of venetoclax shall be consulted in the process of decision making for continuation of the trial.

The dose-escalation part may be followed by an expansion part with enrollment of 42 patients. The decision to proceed to the expansion part will be taken and documented in consultation within

the steering committee after consideration of all available study data during the dose escalation part of the study. These results of data to safety and tolerability of the therapy during the escalation part will be submitted as a substantial amendment to the competent authority and ethics committee for approval the recommended phase-2 dose (RP2D). Patients who achieve a CR/CRp ( $ANC \geq 1 \times 10^9/L$ ) may receive venetoclax maintenance treatment at 400 mg QD p.o. continuously for up to one year. Dose reduction rules will be defined in case toxicities occur. Patients eligible for allogeneic stem cell transplantation with a suitable donor can proceed to transplantation and will be excluded from further study therapy but will further be observed during follow-up period.

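### Section 4.1 makes relapse from remission a criterion for both parts, so as written it bars the primary refractory patients whom the expansion part is meant to admit

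*Protocol*

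**What the plan says.** **Section 4.1, common list.** Under the heading "Inclusion criteria for both escalation and expansion phase", the only disease-status item is "Relapsed from first or second CR after 1-2 cycles of standard induction chemotherapy". It ends with "including relapse after allogeneic stem cell transplantation (dose escalation and expansion part", so the item itself states that it covers both parts. It offers no alternative for refractory disease.

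**Section 4.1, expansion list.** Under "Inclusion criteria applying for expansion phase (Phase II) only", the item begins "Primary refractory after 1-2 cycles of standard induction chemotherapy" and continues, after an *or*, with the same relapse wording as the common list. Nothing says that it replaces the common item.

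**Synopsis.** The target population covers both relapsed patients and those primary refractory to standard induction. The main inclusion criteria nevertheless use the same two-list structure, with relapse in the common list, and refer to section 4.1 for the exact list.

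**Section 1.4.** Patients refractory to standard-dose cytarabine "are therefore excluded from enrolment in the escalation part, but not in the expansion part where higher cytarabine doses will be administered".

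**Section 3.1.** The phase I dose-escalation study is described as being in subjects with "a histologically or cytologically confirmed acute myeloid leukemia who are refractory or suffered a relapse".

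**Section 6.6.** Eligibility is checked on day 1 before the first venetoclax dose. A patient whose eligibility cannot be confirmed is a screening failure.

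**The concern.** Inclusion criteria are normally cumulative: a patient must meet every item that applies to the part being entered. Read that way, the refractory branch of the expansion item can admit nobody, because the common list already demands a prior remission and a relapse. The criteria then define a relapse-only expansion cohort, while the title, the target population and section 1.4 describe a relapsed or refractory one.

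Two things are at stake. The first is conduct: a site that applies the common list turns refractory patients away, and a site that follows the expansion list enrols them against a written criterion. The second is interpretation: the single confirmatory test pools all patients into one CR/CRi rate, so the eligibility text should say plainly who is in that pool.

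**Working it through.** The main check is logical and needs no figures. A short calculation follows, to see whether the design numbers depend on the point.

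**1. The criteria as logic.** Let R = relapsed from first or second CR, and F = primary refractory (no remission reached, so R is false).

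- Common item, both parts: R
- Expansion item: F or R
- Expansion with both lists applied: R and (F or R) = R
- Expansion if the second list replaces the common item: F or R

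| Candidate for expansion | Common item | Expansion item | Both lists applied | Expansion item alone | Intent (synopsis, section 1.4) |
|---|---|---|---|---|---|
| Relapsed after first or second CR | met | met | eligible | eligible | eligible |
| Primary refractory | not met | met | not eligible | eligible | eligible |

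The readings differ in exactly one row. Only the replacement reading matches the stated intent, and the text does not state it.

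**2. Does another section resolve it?**

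- The tag on the common item works against treating its placement as a slip, since it names expansion expressly.
- The synopsis has the same structure and defers to section 4.1.
- Section 1.4 gives the intent: refractory patients are "excluded from enrolment in the escalation part, but not in the expansion part". It is rationale text, however, and not the list against which eligibility is confirmed.
- Section 3.1 departs from section 1.4 in the other direction, describing the escalation part as including refractory patients.

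**3. What follows for a refractory patient.** Under section 6.6, the patient is a screening failure if the common list is applied. If the patient is enrolled anyway, section 11.1 requires strict adherence and a documented explanation of any deviation. The analysis sets do not settle the matter: the full analysis set (8.2.2.1) is defined by exposure at the MTD and the per-protocol set (8.2.2.2) by dose received. A refractory patient enrolled against the common item would therefore remain in the primary analysis.

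**4. Do the phase II numbers depend on this?** Inputs from section 8.2.1 and the synopsis: null rate 0.45, alternative 0.65, one-sided 5%, power 80%, n = 42, rejection at 25 responders. With X binomial(42, p):

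- P(X ≥ 25 | p = 0.45) = 0.0415, within 5%
- P(X ≥ 25 | p = 0.65) = 0.818, above 80%
- P(X ≥ 24 | p = 0.45) = 0.077, so 24 would be too few
- n = 40 with 24 responders gives power 0.798, and n = 41 with 25 gives 0.762, so both fall short

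The stated design reproduces. Disease status is not an input, so moving the criterion changes neither n = 42 nor the threshold of 25.

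**5. Can a power effect be computed?** With refractory share f and response rates p_R (relapsed) and p_F (refractory), the pooled rate is (1 − f)·p_R + f·p_F. The protocol gives none of f, p_R and p_F. Any power figure would only reflect values chosen for the illustration, and it would measure case mix, not the conflict between the two lists.

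**The case against.** The strongest reply is that the intent is already clear. The synopsis names primary refractory patients, section 1.4 says where they may and may not enter and why, and the expansion item is a complete disease-status criterion that restates the whole relapse branch. Read cumulatively it would be redundant, so its only sensible function is to be the phase II rule. The synopsis copy adds little, since it defers to section 4.1, and section 3.1 is an overview that opens no route to enrolment. Nothing in the protocol shows that sites would in fact differ.

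Much of this stands. It shows what the sponsor most likely means, which makes the fix uncontroversial, and divergent handling across the ten planned sites (three plus seven, section 3.6) is a risk, not a demonstrated effect. It does not make the criteria correct. Eligibility is confirmed against the list, and the list expressly applies the relapse item to expansion. Section 1.4 is also not wholly uniform, since one of its paragraphs describes the study population simply as patients with relapsed AML.

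A reader might go further and infer that the 45% benchmark is left without a defined population. The protocol does not support that: section 1.1 gives the 40-55% CR rates for relapsed or refractory AML, and section 8.2.1 says the benchmark comes from trials in this patient population. The 65% rate is argued from combinations in newly diagnosed or de novo AML and is not tied to a relapsed/refractory split.

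**Conclusion.** The point holds as an internal contradiction in the operative eligibility text. As written, section 4.1 excludes from expansion every primary refractory patient, a group that the synopsis, section 1.4 and the expansion list itself mean to include. This rests only on the usual reading that all applicable inclusion criteria must be met.

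The number of the 42 patients affected is unknown. A reader might infer a loss of power from admitting or barring refractory patients, but no such loss can be computed from the protocol, and none is claimed. The sample size, the 25-of-42 rule and the 45% null stand. The correction should be made before expansion opens, because afterwards each refractory patient has either been turned away or entered as a deviation.

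**What to change.** - In section 4.1 and in the synopsis, move the relapse-only item from the common list to a new escalation-only list and delete its tag for the expansion part.
- Keep the primary refractory or relapsed item as the sole disease-status criterion for expansion.
- Reconcile the population description in section 3.1 with section 1.4.
- While the escalation list is being rewritten, also reconcile it with section 1.4's restriction of that part to patients relapsing more than 90 days after previous cytarabine, which appears in neither section 4.1 nor section 4.2.

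This carries out the protocol's own stated intent and sets no new rule. The cost is wording. Section 12 lists changes to inclusion and exclusion criteria among those needing ethics committee and authority approval, and section 3.1 already requires a substantial amendment before expansion, so one submission can carry both. No recalculation is needed.
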